### **8.3.5 Concomitant Medications**

Concomitant medication logs will be completed at the Screening visit and will be updated at each subsequent visit. The logs will include the medication taken by the subject over the past 3 months. A separate log will record anti-PD medications that were previously used.

### **8.3.6 Adverse Events**

Adverse events will be recorded after the signing of the informed consent of enrolled subjects throughout the study and shall be reviewed and updated at each subsequent visit and during any phone contact with the subject. AEs for screen failure subjects will be captured only in the source documents and not in the eCRF.

### **8.3.7 Sleepiness**

Sleepiness will be evaluated at baseline and at end of weeks 5, 8 and 12/Treatment Termination visit (visits 4, 5 and 6) using the Epworth Sleepiness Scale (ESS, see Appendix III).

### **8.3.8 Impulsive-Compulsive Disorders**

The questionnaire for Impulsive-Compulsive Disorders in Parkinson's Disease, (QUIP-Rating Scale Appendix VI), will be used on the baseline visit and at end of weeks 3, 5, 8, 12/Treatment Termination visit and end of week 14 (visits 3, 4, 5, 6 and 7). The answers for all questions are based on current behaviors and behaviors occurred in the past 4 weeks.

### **8.3.9 Suicidality**

Columbia Suicide Severity Rating Scale (CSSRS, see Appendix VIII) will be used. Baseline / screening version of the CSSRS will be used at screening visit. This version assesses suicidality in a patient's lifetime and during the past six months. The Since Last Visit (SLV) version of the CSSRS will be used at all consequent visits. This version assesses suicidality since the patient's last visit. Efforts must be made to ensure that the same trained team member completes this questionnaire for each subject.

A subject with any suicidal ideation that answered YES to questions 4 or 5 in the CSSRS questionnaire will be referred to a mental health professional.

CSSRS-SLV will be used on the baseline visit and at end of weeks 3, 5, 8, 12/Treatment Termination visit and end of week 14 (visits 3, 4, 5, 6 and 7).

## **8.4 Efficacy**

Efforts must be made to ensure that the same Investigator completes the UPDRS, CGI-S and CGI-I scales at all visits that these scales are done.

### **8.4.1 UPDRS – see Appendix IX**

The UPDRS assesses motor and functional abilities of the subjects. The total UPDRS is defined for this study as the sum of Parts II and III (Activities of Daily Living and Motor sections). These will be completed by history and examination. UPDRS II and III will be performed at baseline visit and at end of weeks 5, 8 and 12/Treatment Termination (visits 4, 5, and 6). UPDRS part III will be completed also at screening visit to support diagnosis and the score will be included in the RAF.

The UPDRS part III evaluation will be conducted by a trained neurologist or other senior trained research staff with at least 10 years' experience in conducting the UPDRS. All attempts will be made to ensure that the same trained research staff member performs the UPDRS part III at all visits for each subject and at approximately the same time of the day and time following administration of medication. The UPDRS part II will be completed by a trained neurologist or other trained research staff member as delegated by the Site PI. For consistency efforts must be made to ensure that the same trained research staff member will do the UPDRS part II at all required visits for all subjects.

### **8.4.2 Clinical Global Impression - severity (CGI-S) - Appendix IV**

This scale will be completed by the Investigator at baseline and at end of week 12/Treatment termination (visit 6). The scale rates the subject's overall well-being, including the Parkinson's

disease symptoms over the week before the visit. The CGI scale refers to the global impression of the subject and requires clinical experience with the syndrome under assessment. The CGI-S scale is a 7-point scale that requires the clinician to rate the severity of the subject's illness at the time of assessment, relative to the clinician's past experience with patients who have the same diagnosis. Considering total clinical experience, a subject is assessed on severity of illness at the time of rating using a nominal scoring system with: 1, normal, not at all ill; 2, borderline ill; 3, mildly ill; 4, moderately ill; 5, markedly ill; 6, severely ill; or 7, extremely ill. Efforts must be made to ensure that the same neurologist performs the CGI-S at all visits.

#### **8.4.3 Clinical Global Impression of Improvement (CGI-I) – Appendix XIV**

This scale will be completed by the Investigator at end of weeks 5, 8 and 12/Treatment Termination (visits 4, 5 and 6). The scale rates the subject's overall well-being, including the Parkinson's disease symptoms over the week before the visit.

The CGI-I scale is a 7-point scale that requires the clinician to rate the improvement of the subject's illness relative to the baseline visit using a nominal scoring system with: 1, very much improved; 2, much improved; 3, minimally improved; 4, no change; 5, minimally worse; 6, much worse; or 7, very much worse. Efforts must be made to ensure that the same neurologist performs the CGI-I at all visits.

#### **8.4.4 Quality of Life PDQ39 – Appendix X**

This is a PD specific health-related quality of life scale that will be performed at baseline visit and at end of week 12/Treatment Termination (visit 6). There are 39 questions in the PDQ-39, with 8 discrete scales:

- mobility (10 items)
- activities of daily living (6 items)
- emotional well-being (6 items)
- stigma (4 items)
- social support (3 items)
- cognitions (4 items)
- communication (3 items)
- bodily discomfort (3 items)

Subjects are asked to think about their health and general well-being and to consider how often in the last month they have experienced certain events (e.g. difficulty walking 100 yards).

Subjects are asked to indicate the frequency of each event by selecting one of 5 options (Likert Scale): ever/occasionally/sometimes/often/always or cannot do at all.

#### **8.4.5 Health-Related Quality of Life (HRQOL) SF-12v2 questionnaire – Appendix VII**

The HRQOL SF-12v2 questionnaire assesses the physical and mental health of the patient using 12 questions related to eight aspects of health (physical and social functioning, role limitation

due to physical limitation, vitality, role limitation due to emotional problems, bodily pain, mental and general health). This questionnaire will be filled in on the baseline visit and at end of week 12/Treatment Termination (visits 2, and 6).

## **8.5 Compliance**

### **8.5.1 Study Compliance**

At each study visit the Investigator and/or site coordinator will assess the subject's compliance with the prescribed regimen for the study medication using pill counts. This will include checks of protocol compliance and use of study drug in order to assess the reliability of subject-generated data. Subjects who fail to comply with the study requirements may be withdrawn from the study, following consultation with the sponsor.

The Investigator and clinical staff will make all efforts to ensure all enrolled subjects attend all study visits. If a subject missed a visit all efforts will be made to reschedule the visit within the time frame allowed in this protocol, which is 28±2 days from the previous visit. In case the subject cannot complete the visit in the appropriate time, the subject will continue to the next routine visit. If safety issues arise, an unscheduled visit may be done.

The Investigator and clinical staff will make all efforts to ensure all subjects' efficacy and safety scales are fully completed at each visit. If it is discovered that data is missing from these scales after they were initially completed, the Investigator or a member of the clinical staff can contact the subject, up until the following routine visit, to obtain this missing data. If missing data is not collected by the time of the following routine subject visit, no additional follow-up will be permitted, and this data will be considered missing. Details regarding the collection of this missing data (including time, date, data points collected and who collected them) will be documented in the source documents and the eCRF.

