## 5.2 Dose Modification

Subjects may be allowed to miss a dose of study medication if:

- 1) Subject develops an adverse event that the Investigator believes requires the subject's dose to be held temporarily, or
- 2) Subject loses their kit of study medication and a replacement kit is requested, in this situation the PI should request an emergency shipment to alert the distributor to ship the replacement kit urgently).

During the pramipexole ER titration phase, the PI or sub-Investigator may modify (up or down) subject's dose to either 1.5, 3.0 or 4.5 mg of the pramipexole ER/identical placebo to reach the optimal tolerated therapeutic dose. Following the titration phase, after week 6, no modifications are allowed.

If the subject experiences intolerable adverse events, dosing may be held temporarily or withdrawn (all treatments, including both capsules and tablets, please note that pramipexole

ER/matching placebo tablets need to be down titrated gradually (see down titration instructions in section 6.1). However, the subject will continue to be followed-up according to the protocol pre-planned schedule of activities

No other dose modifications will be allowed in this study.

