### **9.2.6 Visit 4**

Visit 4 will take place 5 weeks after the baseline visit  $\pm 2$  days. The following activities will be performed:

- Evaluation of the pramipexole ER/placebo dose which may be changed if necessary only until the end of the next week, week 6.
- Vital signs (HR, BP RR and temperature) and weight
- Concomitant medications
- Adverse events review

- Study drug accountability
- Collection of the titration kit, (Weeks 1-4)
- UPDRS II, III
- CSSRS-SLV questionnaire
- QUIP-RS questionnaire
- ESS questionnaire
- CGI-I questionnaire
- Orthostatic hypotension scale question 1 for subjects with OH
- Laboratory tests for hepatic or renal function for subjects with mild hepatic failure or mild kidney failure respectively.

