### **9.2.7 Visit 5**

Visit 5 will take place 8 weeks after the baseline visit and start of medication treatment  $\pm 2$  days. The following activities will be performed:

- Vital signs (HR, BP RR and temperature) and weight
- Concomitant medications
- Adverse events review
- Study drug accountability
- Collection of the maintenance kit (Box 1 of 2, weeks 5-8)
- UPDRS II, III
- CSSRS-SLV questionnaire
- QUIP-RS questionnaire
- ESS questionnaire
- CGI-I questionnaire
- Orthostatic hypotension scale question 1 for subjects with OH
- Laboratory tests for hepatic or renal function for subjects with mild hepatic failure or mild kidney failure respectively.

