### **9.2.8 Visit 6 – Treatment Termination**

Visit 6 will be performed at the end of the treatment phase, 12 weeks  $\pm 2$  days after the baseline visit. The following activities will be performed:

- Vital signs (HR, BP RR and temperature), weight
- Concomitant medications
- Adverse events review
- Study drugs accountability
- Collection of maintenance kit (Box 2 of 2 Weeks 9-12)
- UPDRS II and III questionnaire
- CSSRS-SLV questionnaire

- CGI-S questionnaire
- CGI-I questionnaire
- PDQ39 questionnaire
- ESS questionnaire
- QUIP-RS questionnaire
- HRQOL SF-12v2
- Orthostatic hypotension scale question 1 for subjects with OH

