### **9.2.9 Visit 7 – Safety Follow Up**

A follow up safety visit will be performed 2 weeks  $\pm$ 2 days after the termination visit. Safety parameters will be evaluated, as follows:

- Symptom-directed physical and neurological examination
- Vital signs (HR, BP RR and temperature), weight and ECG
- Concomitant medications
- Adverse events review
- Study drugs accountability
- Collection of down titration kit (week 13)
- Laboratory tests, including hematology, chemistry , urinalysis and a serum pregnancy test for women of childbearing potential (see Appendix II)
- CSSRS-SLV questionnaire
- QUIP-RS questionnaire

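### The missed-visit rule of 28±2 days from the previous visit fits only one of the five scheduled intervals, and could place a missed Week 5 visit after dose changes are barred

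*Protocol*

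**What the plan says.** Section 8.5.1 (Study Compliance) gives one rule for any missed visit: staff are to "reschedule the visit within the time frame allowed in this protocol, which is 28±2 days from the previous visit". It then adds a fallback: "In case the subject cannot complete the visit in the appropriate time, the subject will continue to the next routine visit".

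The visit sections and Appendix I set unequal intervals:

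- Visit 3 is at the end of week 3 (section 9.2.4; day 21 ±2 in Appendix I).
- Section 9.2.6: "Visit 4 will take place 5 weeks after the baseline visit" (day 35 ±2).
- Section 9.2.7: "Visit 5 will take place 8 weeks after the baseline visit and start of medication treatment" (day 56 ±2).
- Section 9.2.8: "Visit 6 will be performed at the end of the treatment phase, 12 weeks" after baseline (day 84 ±2).
- Section 9.2.9: "A follow up safety visit will be performed 2 weeks" after the termination visit (day 98 ±2 in Appendix I).

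Section 9.2.1 itself describes visits 2 to 6 as 3 to 5 weeks apart.

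Two passages tie visit 4 to the titration deadline. The activity list in section 9.2.6 opens with "Evaluation of the pramipexole ER/placebo dose which may be changed if necessary only until the end of the next week, week 6". Section 5.2 states: "Following the titration phase, after week 6, no modifications are allowed". The synopsis text on titration visits says the same.

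**The concern.** Section 8.5.1 presents 28±2 days as the protocol's existing visit window, but that window appears nowhere in the schedule. A site that follows 8.5.1 after a missed visit would, for most visits, hold the replacement outside the window set by section 9.2 and Appendix I.

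Two things are at stake. First, visit 4 is the last scheduled evaluation of the tablet dose, and the rule allows it on a date when the dose can no longer be changed. Second, visits 4 and 5 supply the Week 5 and Week 8 UPDRS and ESS values, which the repeated-measures model treats as categorical weeks. A value labelled Week 5 but taken close to Week 8 is not the measurement that the model's time factor describes.

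**Working it through.** **Inputs.** Rule: 26 to 30 days after the previous visit (section 8.5.1). Schedule: baseline as day 0, then days 21, 35, 56, 84 and 98, each ±2 (Appendix I; sections 9.2.4 to 9.2.9). Last date for a dose change: end of week 6, 6 × 7 = day 42 (sections 5.2 and 9.2.6).

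**Step 1: where the 28-day figure does hold.** Visit 5 to visit 6: 84 − 56 = 28. From a visit 5 on day 56, the rule gives 56 + 26 to 56 + 30 = day 82 to 86, the same as the scheduled window.

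**Step 2: all five intervals.** The smallest possible gap is (next day − 2) − (previous day + 2); the largest is (next day + 2) − (previous day − 2). Baseline has no window. The rule's dates are the earliest previous date + 26 to the latest previous date + 30.

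| Interval | Nominal gap | Possible gap | Reaches 26–30? | Date under the rule | Scheduled window |
|---|---|---|---|---|---|
| Visit 2 to 3 | 21 | 19–23 | no | 26–30 | 19–23 |
| Visit 3 to 4 | 14 | 10–18 | no | 45–53 | 33–37 |
| Visit 4 to 5 | 21 | 17–25 | no | 59–67 | 54–58 |
| Visit 5 to 6 | 28 | 24–32 | yes | 80–88 | 82–86 |
| Visit 6 to 7 | 14 | 10–18 | no | 108–116 | 96–100 |

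Four of the five gaps cannot reach 26 days even with both windows at their extremes. Taking baseline as day 1, as Appendix I labels it, changes only the first row (gap 20, possible 18–22, rule date 27–31) and not the conclusion.

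**Step 3: visit 4 against the dose deadline.** With visit 3 on day 19 to 23, the rule gives 19 + 26 = 45 to 23 + 30 = 53. Relative to day 42 this is 45 − 42 = 3 to 53 − 42 = 11 days late. The Week 8 window opens on day 54, so the latest date is 54 − 53 = 1 day before it.

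**Step 4: other readings of the rule.**

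- *Within* as an upper limit only: a missed visit 4 may be held from day 38. Days 38 to 42 precede the deadline; days 43 to 53 do not.
- Week 4 phone call (day 28 ±2) as the previous visit: 26 + 26 = 52 to 30 + 30 = 60, later still.
- Visit 3 also missed, counting from baseline: day 26 to 30. This is before the Week 5 window opens on day 33, so the rule still conflicts with the schedule, but the visit is not after the deadline.

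**Step 5: which mismatches touch the efficacy data.** Appendix I collects UPDRS parts II and III and the ESS at visits 4, 5 and 6 after baseline, and at neither visit 3 nor visit 7. The mismatches that can reach the model are therefore those at visits 4 and 5.

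**The case against.** The strongest case on the other side is that this is one stray figure in a compliance section. Visit-specific windows are stated twice, in section 9.2 and in Appendix I, and the primary and ESS contrasts are tested at Week 12, where rule and schedule agree. Sections 15.1 and 15.6.8 still refer to weeks 4, 8 and 12 where the synopsis says 5, 8 and 12. The 28-day figure may be left over from a four-weekly schedule, though that is an inference.

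Much of this stands. A reader might go further than the documents allow in four ways:

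- *That a missed visit 4 would necessarily fall after the dose deadline.* On the upper-limit reading it only could. Dose is also evaluated at visit 3, at the Week 4 call and at unscheduled titration visits, and a late visit 4 does not lift the bar on changes.
- *That lateness passes from visit to visit.* The rule applies only to a missed visit, and visits 4, 5 and 6 are each counted from baseline. Only consecutive missed visits would carry it forward: a visit 5 on day 59 to 67 followed by a missed visit 6 would give 59 + 26 = 85 to 67 + 30 = 97.
- *That mislabelled weeks would enter the model.* SAP version 2.0 is not among the documents. Its addendum distinguishes scheduled from unscheduled visits, so a windowing rule may exist.
- *That the Week 12 comparison is compromised.* Week 5 and Week 8 values inform the Week 12 estimate only through the covariance model.

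The fallback to the next routine visit does not remove the conflict. It applies once the appropriate time has passed, and that time is the same 28±2 days.

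**Conclusion.** The inconsistency is real: the rule fits one of five intervals, and the ±2-day windows do not close the gap for the other four. After an on-time visit 3, a missed visit 4 is allowed on day 45 to 53. The dose evaluation could then come 3 to 11 days after changes are barred, and a Week 5 UPDRS or ESS could be taken as little as one day before the Week 8 window. A missed visit 5 could be held up to 67 − 58 = 9 days after its window closes.

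The effect is confined to missed visits. The documents do not say how many are expected, so no bias can be put in figures. With visit 5 on day 56, the rule leaves the Week 12 visit where the schedule puts it; with visit 5 elsewhere in its window, the difference is at most 2 days at either end.

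This rests on counting the five intervals between clinic visits 2 to 7, and, for visit 4, on visit 3 having taken place and being the previous visit. It is worth correcting because sites act on this sentence, but it does not by itself undermine the primary analysis.

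**What to change.** Reconcile section 8.5.1 with section 9.2, Appendix I and the titration text, so that a missed visit is referred to that visit's own window. Visit 7 should stay counted from the termination visit, as in section 9.2.9. No dose rule is proposed here; how a late visit 4 relates to the week 6 limit is for the sponsor to settle when reconciling the passages.

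Separately, confirm that SAP version 2.0 assigns each UPDRS and ESS assessment to an analysis week by actual study day, and add such a rule if it does not.

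The cost is one sentence in the protocol and, if needed, one rule in the SAP. The downside is that a few very late assessments would not count for their nominal week.

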## **8.6 Screening Evaluations**

The following scales or tests will be used for screening evaluations:

- UK Parkinson's Disease Society Brain Bank Clinical Diagnostic Criteria – (Appendix XI) will be used to confirm the Parkinson's disease diagnosis.
- Modified Hoehn & Yahr Stage (Appendix XII) The scale should be completed with the Investigator rating PD symptoms to confirm that the subject meets inclusion criteria related to stage of disease.
- Mini-Mental State Examination (MMSE) (Appendix XIII) MMSE, a 30 points questionnaire, will be completed to evaluate the subject for cognitive abilities necessary for study participation.
- Columbia Suicide Severity Rating Scale - baseline, CSSRS-BL, (Appendix VIII)
- UPDRS part III (Appendix IX)

## **9 STUDY CONDUCT**

### **9.1 Study Period**

The study duration per subject is 14 weeks in addition to up to 28 days for screening. The whole study duration is expected to be approximately 18-24 months.

### **9.2 Study Procedures**

#### **9.2.1 Detailed Study Plan**

A detailed Schedule of Activities is provided in Appendix I.

The study includes 7 visits. The first visit will allow screening of potential subjects that will participate in the study. This period of time between the screening visit and enrollment of a subject to the study is named the screening phase. The treatment phase is when subjects are receiving treatment with the study drugs. During the treatment phase, subjects' condition will be evaluated every 3-5 weeks (visits 2-6). The first 6 weeks of the treatment period will include a titration of the Pramipexole ER dose or its placebo to optimal dose (titration phase). One capsule a day of P2B001/PPX 0.6/RAS 0.75/Placebo will be taken at this time without any need for titration. This will be followed by a maintenance phase ending at the end of week 12. The safety follow up phase will start after week 12 which will include a week (week 13) of no treatment of the P2B001 or its components and a down-titration of pramipexole ER or its placebo. Week 14 will include no treatment at all. The end of the study drug treatment and a follow up safety visit will be performed at the end of week 14 (visit 7).

#### **9.2.2 Visit 1 - Screening Visit**

Prior to performing any study activity, the subject will be thoroughly informed on all aspects of the study. The subject will be requested to sign an Ethics Committee/investigational Review Board (EC/IRB) approved informed consent form, after which a unique subject number will be assigned to the subject.

Adverse events will be recorded after the signing of the informed consent of enrolled subjects.

Subjects will be assessed for study eligibility by the Investigator at the screening visit.

Subject eligibility will be assessed based on clinical procedures:

- Medical history – Complete medical history including PD history
- Complete physical and neurological examination
- Vital signs (HR, BP RR and temperature), height, weight, and ECG
- Previous and concomitant drug history (record of drugs used 3 months prior to study)

- Laboratory tests, including hematology, chemistry, urinalysis, coagulation and a serum pregnancy test for women of childbearing potential (see Appendix II)
- Mini Mental State Exam (MMSE)
- Modified H&Y staging
- UPDRS part III
- UK Parkinson's Disease Society Brain Bank Clinical Diagnostic Criteria
- CSSRS-BL

After completion of all the testing for the assessment of eligibility, it will be decided by the Investigator whether the subject is eligible for the study. For a subject to be eligible all the inclusion criteria must be met and none of the exclusion criteria must apply. Therefore, all the results from the screening procedures must be available before determining a subject's eligibility. Subjects found eligible will be further reviewed by a central eligibility monitoring committee (see 16.4.2). The maximal interval between the screening and baseline visits is 28 days that can be extended up to 35 days, however, additional Sponsor approval will be required. Extension beyond 35 days and up to 90 days may be approved but will require a new collection of screening laboratory samples at an unscheduled visit prior to baseline. Subjects that are screen failures may rescreen for the study. If the rescreening visit is within 28 days (or 35 days with sponsor approval) of the original blood testing, the screening number remains the same and the blood draw does not need to be repeated, unless it is the reason for the screening failure. Subjects complying with inclusion/exclusion criteria will be randomly assigned to one of the four treatment groups by a central website-based computer program using Randomization Trial Supply Management (RTSM). A randomization form must be completed via the RTSM as soon as possible after subject eligibility was confirmed in order to trigger shipment of investigational product for this subject.

